During the study, subjects in Group 1 will continue use of antimycobacterial treatment. All changes in antimycobacterial treatment will be recorded, including reasons for each change. In case of worsening of NTM pulmonary disease, antimycobacterial treatment may be added or a dosage increase of antimycobacterial treatment may be applied as rescue treatment, according to investigator's discretion.

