### **12.3. Prior and Concomitant Medication**

The subject's use of all concomitant medication must be recorded in the eCRF.

All relevant prior medication should also be recorded. This includes the most recent course of antimycobacterial treatment taken within 3 years prior to the screening visit. Other prior medication should also be recorded if considered relevant by the investigator. Standard information about the medication will be collected including the name of medication, dose, frequency, administration route and treatment period.

Changes to medication not provided as a part of this trial should be kept to a minimum during the trial. However, if considered necessary for the subject's well-being concomitant medication may be given at the discretion of the investigator according to local standard care. All changes will be recorded, including reasons for each change.

In case of worsening of NTM pulmonary disease, antimycobacterial treatment may be added or a dosage increase of antimycobacterial treatment may be applied as rescue treatment, according to investigator's discretion.

At each visit the investigator should ask the subject about use of concomitant medication. All concomitant medication must be documented in the subject's medication records and in the eCRF. Furthermore, each change in concomitant medication (e.g. new treatment, discontinuation of treatment and change in dosage/routine) during the trial must be documented in the same way.

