Subjects that do not wish to continue to 48 weeks of treatment will end treatment after 24 weeks (visit 8) and will attend the follow-up visit 12-weeks later as per the visit schedule outlined in Protocol Version 2.0 or 3.0.

Subjects who complete the initial 24-week treatment period prior to the approval of Protocol Version 4.0 will proceed to the 12-week follow up as per the visit schedule in Protocol Version 2.0 or 3.0. Once Protocol Version 4.0 is approved they will be asked to re consent and re-initiate treatment. This will occur at the next trial visit or at an unscheduled visit. These subjects will not receive the whole 48-week treatment. They will receive treatment for an additional 24 weeks minus the number of weeks that they have been in follow up.

Subjects that do not wish to re consent and re initiate treatment will stay in follow up and attend the follow-up visit as per the visit schedule outlined in Protocol Version 2.0 or 3.0.

At Baseline and at Weeks 4, 12, 24, 32 and 40 (Visits 2, 3, 5, 8, 10 and 12), dosing will take place in the clinic after blood sampling. A data review was conducted after the first 6 subjects had completed 12 weeks of treatment. If safety concerns or poor tolerability were identified in this review, the review committee might decide on less frequent dosing for subsequent subjects in the study. The review was conducted on 16 September 2018 and concluded that there were no safety issues of significant concern and the dose was unchanged. In order to obtain more robust treatment responses it was decided to extend the treatment duration from 24 to 48 weeks. Any changes to the conduct of the study such as change of dose, dose regimen or duration will be documented in a protocol amendment.

During the study, subjects in Group 1 will continue use of antimycobacterial treatment. All changes in antimycobacterial treatment will be recorded, including reasons for each change. In case of worsening of NTM pulmonary disease, antimycobacterial treatment may be added or a dosage increase of antimycobacterial treatment may be applied as rescue treatment, according to investigator's discretion.

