9.2 Variables

9.2.1 *Primary Endpoint Variables*

- Sputum culture conversion during the treatment period defined as all available samples from three consecutive visits to be negative
- The time of culture conversion: Defined as the time the first of three consecutive visits with 100% negative samples was obtained. Subjects with no conversion will be censored at the date of their last visit.

9.2.2 *Secondary Endpoint Variables*

- Sputum smear conversion: Defined as at least three consecutive visits with 100% negative AFB stained sputum smears on microscopy during the treatment period in subjects that were smear positive at Baseline.
- Durability of sputum culture conversion: Defined as conversion at or before Week 48 and culture still negative at 12-weeks follow-up (with no positives in between).
- Durability of sputum smear conversion: Defined as conversion at or before Week 48 and smear still negative at 12-weeks follow-up (with no positives in between).
- Change from baseline in semi-quantitative grade of number of NTM on microscopy of AFB stained sputum smears
- Change from baseline in semi-quantitative grade of sputum cultures (measured by time to positivity and exploratory quantitation of cultures)
- Change from baseline in symptom scores
 - Lower Respiratory Tract Infections – Visual Analogue Score (LRTI-VAS)
 - Quality of Life Questionnaire – Bronchiectasis (QOL-B)
- Change from baseline in Global Rating of Health (GRH)
- Change from baseline in body weight
- Change from baseline in 6MWD, oxygen desaturation and Borg CR10 scores

9.3 **Biostatistical methods**

9.3.1 *Primary Endpoint*

9.3.1.1 *Sputum Culture Conversion*

Sputum culture conversion data will be listed, including time of culture conversion.

Sputum culture conversion rates (number of subjects who convert to negative out of the number per group) will be presented with 95% exact binomial confidence intervals.

On the basis of the poor historical success rates of current standard therapy, a 30% response rate for the primary endpoint will be considered clinically relevant.

Time to culture conversion will be evaluated using Kaplan Meier estimates, with 95% confidence intervals.

9.3.1.2 *Sensitivity Analyses*

In a sensitivity analysis, culture conversion will be re-defined as requiring at least 2 samples are available from each of the three consecutive visits. Sputum culture conversion rates and time to culture conversion will be analysed as part of this sensitivity analysis.

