10.4 Prior and Concomitant Medication

Concomitant therapies will be coded using the World Health Organization-Drug Reference List (WHODRL).

Prior and concomitant medications will be presented in separate listings. Medications stopped on the same day as first study drug administration will be considered as prior medication only. Both prior and concomitant listings will flag antimycobacterial treatments and include data related to changes of the patient's NTM treatment regimen and the reason for a change to patient's NTM treatment regimen.

Prior and concomitant medication summaries will be presented in separate tabulations, with data summarised by Anatomical Therapeutic Chemical (ATC) (Level 2) and Preferred Name (PN) using frequency counts and percentages. For the summaries of prior and concomitant medications, subjects who take the same medication (in terms of the PN) more than once will be counted only once for that medication. An additional concomitant medication table will be prepared to present antimycobacterial treatments.

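### Culture conversions reached after antimycobacterial treatment is added or increased count in the primary rate, and no planned analysis gives the rate without them

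*SAP*

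**What the plan says.** **Rescue is allowed.** Protocol 12.3 states, without limiting it to one group: "In case of worsening of NTM pulmonary disease, antimycobacterial treatment may be added". It also says that other "concomitant medication may be given at the discretion of the investigator according to local standard care". SAP 2.1 repeats that "antimycobacterial treatment may be added or a dosage increase of antimycobacterial treatment may be applied as rescue treatment", as do the Protocol Synopsis and Protocol 8.1.

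**The endpoint ignores it.** SAP 9.2.1 defines conversion as three consecutive treatment-period visits at which every available sample is negative. SAP 9.3.1.1 reports the "number of subjects who convert to negative out of the number per group" with exact 95% intervals and calls a 30% response clinically relevant. For time to conversion the only censoring rule is: "Subjects with no conversion will be censored at the date of their last visit".

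**The sensitivity analysis concerns something else.** In SAP 9.3.1.2, "culture conversion will be re-defined as requiring at least 2 samples are available from each of the three consecutive visits".

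**The data will exist.** Protocol 8.1 says: "All changes in antimycobacterial treatment will be recorded, including reasons for each change". SAP 10.4 says: "Both prior and concomitant listings will flag antimycobacterial treatments". It adds regimen changes and their reasons to those listings and plans a separate table of antimycobacterials.

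**The concern.** The trial has no control arm, and its primary objective is the efficacy of inhaled molgramostim on culture conversion. When a subject worsens on study drug, receives added antibiotics and then turns culture negative, the plan scores a success. Nothing in the design or the planned analyses separates that success from one reached on the entry regimen.

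This matters most in Group 2, whose subjects enter off a multidrug regimen. A Group 2 subject who starts one stays in Group 2, because SAP 2.4 classifies subjects once, at Baseline. The Group 2 rate would then mix conversions reached with and without antibiotics, although the two groups were formed to give pilot data on each situation separately (Protocol 6.2).

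What is at stake is interpretation. Protocol 6.3 says that the pilot is to inform planning of the later phase II program, and that planning needs to know whether conversions came with or without added antibiotics.

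**Working it through.** The plan states no figure for this point: the 30 subjects rest on no formal calculation, and the 30% is a benchmark without a test. There is nothing to reproduce. The check has three parts.

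**1. Does any planned output give the rate without these conversions?**

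| Place | What it covers | Separates them? |
|---|---|---|
| SAP 9.2.1, definition | All samples negative at three consecutive visits | No |
| SAP 9.2.1, censoring | Non-converters only, at last visit | No |
| SAP 9.3.1.2 | Minimum samples per visit | No |
| SAP 4.1.1 | One analysis set, all enrolled subjects | No |
| SAP 5, critical deviations | Compliance below 80%; no sputum at 2 visits | No |
| SAP 10.4 | Listings with flags and reasons; antimycobacterial table | Not linked to conversion |
| SAP 13 and 14 | Replaced cross-tabulations; interim analysis | No |

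The conversion listing (SAP 9.3.1.1) gives the time of conversion, so a reader could match it by hand with the medication listings. That gives subject-level information, not a prespecified rate. A rate recalculated from it would be post hoc and labelled so under SAP 1.

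**2. What would one such conversion do?** Group sizes are not given, so n = 10, 15 and 20 are assumptions; n = 30 is the planned total, which SAP 3.1 also summarizes. One conversion moves the estimate by 1/n. The counts below are chosen where it reaches or crosses 30%. Intervals are exact (Clopper-Pearson) 95%.

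| n | Without it | With it |
|---|---|---|
| 10 | 2/10 = 20.0% (2.5 to 55.6) | 3/10 = 30.0% (6.7 to 65.2) |
| 15 | 4/15 = 26.7% (7.8 to 55.1) | 5/15 = 33.3% (11.8 to 61.6) |
| 20 | 5/20 = 25.0% (8.7 to 49.1) | 6/20 = 30.0% (11.9 to 54.3) |
| 30 | 8/30 = 26.7% (12.3 to 45.9) | 9/30 = 30.0% (14.7 to 49.4) |

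Every interval contains 30%.

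**3. How often would it have to happen?** Let r be the share of a group with a change early enough to matter, and c the share of those who convert after it. The expected number of such conversions is n × r × c, which equals one when r × c = 1/n.

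| n | 1/n | c needed if r = 20% (assumed) | c needed if r = 10% (assumed) |
|---|---|---|---|
| 10 | 10% | 50% | 100% |
| 15 | 6.7% | 33% | 67% |
| 20 | 5% | 25% | 50% |

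This is a break-even sum. It does not say what r and c are.

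The documents give only indirect hints, and these conflict:

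- *Timing.* Visits are four weeks apart, so the first of three negative visits must fall by Week 40 (40, 44, 48), or by Week 16 (16, 20, 24) if treatment ends at Week 24. Protocol 6.1 says that the last positive culture seldom falls within the first 6 months of therapy (about 26 weeks). Taken literally, a change would have to start by about 40 − 26 = Week 14 in a 48-week course, and a 24-week course leaves almost no room (16 − 26 = −10). This is not a hard limit: the endpoint needs three negative visits and allows later positives.
- *Responsiveness.* Protocol 6.2 expects no response to further NTM treatment in this population and includes those who declined treatment. The same section puts overall treatment success at 40–60%, and never-treated subjects have not shown drug failure.

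**The case against.** The strongest case against has four parts.

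- *The plan is already a treatment-policy rate.* An unconditional definition and a single all-enrolled set lead there, and wanting that said is clarification. This stands: the primary rate is coherent and should not change. What remains is the missing label and the missing companion rate.
- *The information will be in the report.* The conversion and medication listings are planned, and in a trial of 30 they can be read together. This stands for subject-level disclosure. It does not supply a rate whose rule was fixed before anyone saw who converted, which matters in an open-label trial.
- *The study is a descriptive pilot.* No test attaches to 30%, the intervals are wide and the effect may be small. This stands and limits the weight of the point.
- *A rule triggered by any change would be too broad.* It would fail a subject whose drug was swapped for intolerance without escalation. This stands, and the fix excludes such swaps.

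A reader might also infer that the primary rate overstates the effect of molgramostim and that leaving these conversions out would isolate it. The documents do not support that. There is no control arm, Group 1 continues antimycobacterials throughout, and Protocol 6.2 proposes that GM-CSF potentiates antibiotics. Neither rate is attributable to molgramostim.

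**Conclusion.** The point holds as a gap in the planned analyses. Conversions reached after added or increased antimycobacterial treatment count as successes, and no prespecified rate shows the result without them. This follows from the wording of SAP 9.2.1 and 9.3.1.1; the SAP does not say it outright.

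The size cannot be determined from the documents. A reader might infer from the break-even table that the excess is under one subject per group, or from the first table that the 30% benchmark would be met falsely. Neither follows: r, c and the group sizes are assumptions, and the counts were chosen near 30%. What can be said is that, at 10 to 20 subjects per group, one such conversion can carry the point estimate to or past 30%, while the exact interval contains 30% either way.

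The change is worth making because the data are already collected and the cost is low. It is not a correction of the primary endpoint.

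**What to change.** 1. Keep the primary rate. In SAP 9.3.1.1 label it as conversion regardless of changes in antimycobacterial treatment.
2. In SAP 9.3.1.2 prespecify one supplementary culture-conversion rate by group, with exact 95% intervals. A subject is a converter only if all three qualifying negative visits precede the first post-Baseline addition, new start or dose increase of antimycobacterial treatment. A one-for-one substitution for intolerance, with no escalation, does not trigger the rule.
3. Show the same rate when only changes recorded as rescue for worsening NTM disease trigger the rule.
4. Report the number and timing of changes by group, and present the rates side by side.

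Applying the same flag to smear conversion, durability and time to conversion is optional. The rule is an alternative endpoint definition, like the existing sensitivity analysis, so it does not conflict with the no-imputation rule in SAP 12.

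**Cost.** SAP wording and one derived flag from dates and reasons already recorded; no new data, no change to the protocol endpoint and no change to rescue care. The supplementary rate may be conservative. It drops conversions that depend on molgramostim potentiating an added antibiotic, and it drops a subject whose change falls between qualifying visits, for instance after two negative visits and before the third. That is why both rates are needed.

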### 9.1. Subject Inclusion Criteria

1. History of chronic pulmonary infection with MAC or *M. abscessus* (defined as at least 2 documented positive sputum cultures in the prior 2 years, of which at least one was obtained in the 6 months prior to Screening).
2. Subject fulfills one of the following criteria:
  - Subjects who remain sputum culture positive while currently on a multidrug NTM guideline based antimycobacterial regimen, which has been ongoing for at least 6 months prior to the Baseline Visit
  - Subjects who remain sputum culture positive but have either stopped a multidrug NTM guideline based antimycobacterial regimen at least 28 days prior to Screening due to lack of response or intolerance, or never started such treatment.
3. Ability to produce at least 2 mL of sputum or be willing to undergo an induction that produces at least 2 mL of sputum for clinical evaluation.
4. Female or male  $\geq 18$  years of age.
5. Females who have been post-menopausal for more than 1 year or females of childbearing potential after a confirmed menstrual period using a highly efficient method of contraception (i.e. a method with less than 1% failure rate such as combined hormonal contraception, progesterone-only hormonal contraception, intrauterine device, intrauterine hormone-releasing system, bilateral tubal occlusion, vasectomized partner, sexual abstinence), during and until thirty (30) days after last dose of trial treatment. Females of childbearing potential must have a negative serum pregnancy test at Screening (Visit 1) and a negative urine pregnancy test at dosing at Baseline (Visit 2) and must not be lactating.
6. Males agreeing to use condoms during and until thirty (30) days after last dose of medication, or males having a female partner who is using adequate contraception as described above.
7. Willing and able to provide signed informed consent.

---

 Sexual abstinence is considered a highly effective method only if defined as refraining from heterosexual intercourse during the entire period of risk associated with the study treatments. The reliability of sexual abstinence needs to be evaluated in relation to the duration of the clinical trial and the preferred and usual lifestyle of the subject.

8. Willing and able to comply with scheduled visits, treatment plan, laboratory tests, and other trial procedures specified in the protocol as judged by the investigator

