2. PROJECT OVERVIEW

2.1 Study Design

This is an open-label, non-controlled, multicentre, pilot clinical trial of inhaled molgramostim in subjects with persistent pulmonary NTM infection.

The study will comprise a Screening Visit, Baseline Visit, a 48-week treatment period and a 12-week follow up period. The Screening Visit (Visit 1) will be conducted up to 10 weeks prior to the Baseline Visit (Visit 2) to determine eligibility. Adult subjects with a history of chronic NTM infection with at least 2 positive cultures in the prior two years, of which at least one is within the last 6 months prior to Screening, will be considered for enrolment. Subjects should provide a positive NTM sputum culture at Screening to be eligible.

The study will include 30 subjects.

The treatment period will consist of 14 trial visits (Screening, Baseline, and at Weeks 4, 8, 12, 16, 20, 24, 28, 32, 36, 40, 44, and 48; Visits 1-14) and a follow-up visit (Visit 15) 12 weeks after end of treatment. The visits at Weeks 28, 36 and 44 (Visits 9, 11 and 13) will include a telephone contact, all other visits will include a clinic visit.

At the Baseline Visit (Visit 2), eligible subjects will start treatment with inhaled molgramostim administered via the PARI eFlow nebulizer.

At each visit (Visits 1-15), sputum samples for staining and microscopy, and microbiological culture will be collected. If required, induced sputum may be obtained according to local standards. On the days of clinic visits (Visits 1, 2, 3, 4, 5, 6, 7, 8, 10, 12, 14 and 15), subjects will be asked to collect two additional sputum samples at home, preferably on the consecutive days after the site visit (At the commencement of the study, only 1 sample was required for Visits 2 to 7, with the additional sampling added in protocol amendment(s)). On the days of the telephone contact visits (Visits 9, 11 and 13), three sputum samples will be collected at home, preferably on consecutive days.

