3. STATISTICAL CONSIDERATIONS

3.1 Analytical Approach

Data analysis will be performed according to Southern Star Research's Standard Operating Procedures (SOPs).

The general analytical approach for all endpoints will be descriptive in nature. All summaries will present the data by treatment group as well as by all subjects combined.

Unless otherwise stated, the following statistical approaches will be taken:

Continuous variables: Descriptive statistics will include the number of non-missing values, mean, standard deviation (SD), median, minimum, and maximum. The minimum and maximum values will be presented to the same number of decimal places as recorded in the eCRF; mean, median, and SD will be presented to one more decimal place than the raw data.

Categorical variables: Descriptive statistics will include frequency counts and percentages per category. Percentages will be rounded to one decimal place, with the denominator being the number of subjects in the relevant population with non-missing data.

Multiplicity: As this is an exploratory study no adjustments for multiplicity will be applied.

Confidence intervals (CIs): CIs will be two-sided and will use 95% confidence levels. Any analyses requiring significance testing will use a two-sided test at the 5% significance level.

Unscheduled Visits Unscheduled visits will be excluded from summary tables.

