3.3.2 Study Terminology

Study-specific standard terms are detailed in Table 3.

Table 3: Study CDISC Terminology

Subject Elements	Screen (SCRN) Molgramostim (MOLG) Follow-Up (FU)
Epochs	SCREENING OPEN LABEL TREATMENT FOLLOW-UP
Treatment Arms	GROUP 1 GROUP 2
Visit Numbers / Visits	
SCREENING EPOCH
 
1.0 Screening
 
TREATMENT EPOCH
 
2.0 Baseline Visit*
 
3.0 Week 4
 
4.0 Week 8
 
5.0 Week 12
 
6.0 Week 16
 
7.0 Week 20
 
8.0 Week 24
 
9.0 Week 28
 
10.0 Week 32
 
11.0 Week 36
 
12.0 Week 40
 
13.0 Week 44
 
14.0 Week 48
 
888 Early Discontinuation
 
999 End of Study
 
FOLLOW-UP EPOCH
 
15.0 Follow Up Visit
 
Unscheduled visits: x.n where x is the visit number of the closest previous scheduled visit and n is the sequence number of the unscheduled visit, restarting at 1 after each scheduled visit. EPOCH will be assigned according to the epoch of the closest previous visit.
 
* “Baseline Visit” will be used when referring to Visit 2. The term “Baseline” will also be used as detailed in 3.3.3.

3.3.3 **Baseline**

For sputum data, baseline will be derived from the combined pre-treatment visits (i.e. Screening and Baseline), where at least one positive sample will be assigned as positive as baseline. For gradings, the most severe/highest grade will be used.

For all other parameters, baseline will be defined as the last available assessment prior to first study drug administration.

3.3.4 **Change from Baseline**

Absolute change from Baseline will be calculated as:

$$\text{Absolute change from baseline} = (\text{postbaseline value}) - \text{baseline value}$$

3.3.5 **Listings, Tables and Figures**

Listings, tables and figures will be delivered as individual .rtf files in accordance with the mock listings, tables and figures.

Data listings will present all data, with subjects grouped by Group.

Tabulations will summarise data by Group and Total.

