9.1 Endpoints

9.1.1 *Primary Efficacy Endpoint:*

- Sputum culture conversion defined as at least three consecutive negative sputum samples during the treatment period.

9.1.2 *Secondary Efficacy Endpoints:*

- Sputum smear conversion defined as at least three consecutive negative AFB stained sputum smears on microscopy during the treatment period in subjects who were smear positive at Baseline.
- Durability of sputum culture conversion (defined as conversion at or before Week 48 and culture still negative at 12-weeks follow-up).
- Durability of sputum smear conversion (defined as conversion at or before Week 48 and smear still negative at 12-weeks follow-up).
- Change in semi-quantitative grade of number of NTM on microscopy of AFB stained sputum smears from Baseline to Weeks 4, 8, 12, 16, 20, 24, 28, 32, 36, 40, 44, 48 and 12-week follow-up.
- Change in semi-quantitative grade of sputum cultures from Baseline to Weeks 4, 8, 12, 16, 20, 24, 28, 32, 36, 40, 44, 48 and 12-week follow-up.
- Change in symptom scores (assessed using Lower Respiratory Tract Infections – Visual Analogue Scale (LRTI-VAS) and Quality of Life Questionnaire– Bronchiectasis (QOLB) from Baseline to Weeks 4, 8, 12, 16, 20, 24, 32, 40, 48 and 12-week follow-up.
- Change in Global Rating of Health (GRH) from Baseline to Weeks 4, 8, 12, 16, 20, 24, 32, 40, 48 and 12-week follow-up.
- Change in body weight from Baseline to Weeks 4, 8, 12, 16, 20, 24, 32, 40, 48 and 12-week follow-up.
- Change in 6MWD, oxygen desaturation and Borg CR10 scores during a 6MWT from Baseline to Week 12, 24, 48 and 12-week follow-up.

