9.3.2 *Secondary Endpoints*

9.3.2.1 *Sputum Smear Conversion (Primary)*

Sputum smear conversion will be evaluated and presented in the same way as the primary endpoint for culture conversion.

9.3.2.2 *Sputum Smear Conversion (Sensitivity)*

In a sensitivity analysis, smear conversion will be re-defined as requiring at least 2 samples are available from each of the three consecutive visits. Sputum smear conversion rates and time to smear conversion will be analysed as part of this sensitivity analysis.

9.3.2.3 *Mycobacterial Microscopy Grading*

Mycobacterial microscopy data will be listed for each sample, including AFB positivity and AFB semi-quantitative grading. The listing will also include the overall visit AFB positivity and grading statuses. Laboratory grading terminology will be re-named as detailed in Table 4.

Table 4: *Mycobacterial Microscopy Grading*

SNP	RBH	Cross-Tabulation
No acid fast bacilli seen	No AFB Seen	Negative
Acid fast bacilli – occasional	Scanty AFB Seen +/-	Scant
Acid fast bacilli +	Moderate AFB Seen 1+	1+
Acid fast bacilli ++	Moderate AFB Seen 2+	2+
Acid fast bacilli +++	AFB Seen 3+	3+
Acid fast bacilli ++++		4+

The number of subjects who decrease over the scale (and proportion out of the number per group) will be presented with 95% exact binomial confidence intervals.

A summary table will present continuous descriptive statistics of grade for each scheduled visit.

9.3.2.4 *Mycobacterial Culture Grading*

Mycobacterial culture data will be listed for each sample, including culture positivity, culture semi-quantitative grading, time to detection in liquid media (MGIT) and organisms isolated. The listing will also include the overall visit AFB positivity and grading statuses.

The following is noted:

- MGIT and semi-quantitative grading will need to be extracted from the Comment column in the SNP data transfer.
- Semi-quantitative grading is not available for mycobacterial culture data from RBH.

For each scheduled visit, the number of subjects (and proportion out of the number per group) who report a decreased culture grade compared to Baseline will be presented with 95% exact binomial confidence intervals. Where multiple samples were taken at a visit, the worst grade will be used for comparison to Baseline.

A figure will present the mean change from baseline of semi-quantitative sputum culture grades, with error bars representing the standard deviation.

9.3.2.5 *Symptom Scores*

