13. CHANGES TO THE PLANNED ANALYSIS

The following changes to the biostatistical methods planned in the protocol are defined below:

- The 5x5 cross-tabulation summaries of the semi-quantitative grading described in Section 13.2 of the protocol (Secondary Endpoints) has been replaced with alternative summary tabulations, in order to present the data in a clearer and useful way.

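### SAP 9.3.2.3 reports the smear grade-decrease rate only out of the number per group, so any subject who is smear Negative at baseline cannot decrease but stays in the denominator

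*SAP*

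**What the plan says.** SAP 9.3.2.3 specifies the smear summary as follows: "The number of subjects who decrease over the scale (and proportion out of the number per group"), with an exact binomial 95% interval. Protocol 13.2 uses the same denominator. The only analysis set is the Full Analysis Set, meaning all enrolled subjects (SAP 4). In SAP Table 4 the lowest grade is Negative. SAP 3.3.3 derives baseline from Screening and the Baseline Visit combined: "For gradings, the most severe/highest grade will be used".

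Entry rests on culture. Protocol 9.1 asks for chronic infection, "defined as at least 2 documented positive sputum cultures in the prior 2 years", and SAP 2.1 adds: "Subjects should provide a positive NTM sputum culture at Screening to be eligible". No criterion asks for a positive smear. The smear-conversion endpoint, by contrast, is assessed only "in subjects who were smear positive at Baseline" (SAP 9.1.2, and again in 9.2.2).

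Protocol 13.2 paired the decrease rate with a cross-tabulation of baseline grade against visit grade. SAP 13 states: "The 5x5 cross-tabulation summaries of the semi-quantitative grading described in Section 13.2 of the protocol (Secondary Endpoints) has been replaced". Besides the listing and the decrease count, the only summary named in 9.3.2.3 is this: "A summary table will present continuous descriptive statistics of grade for each scheduled visit".

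**The concern.** The plan foresees smear-negative subjects, since it excludes them from smear conversion. It keeps them in the grade-decrease rate, where each one is a certain non-decrease. That rate therefore mixes two things: how often grades fall in subjects whose grade can fall, and how many subjects started with a grade above Negative. Only the first bears on the secondary objective of reducing bacterial load.

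Results are shown by group. Group 1 is on antimycobacterial treatment and Group 2 is not, so their smear-negative shares need not be equal. Two groups with the same response among smear-positive subjects could then show different rates. In the protocol's table, the Negative row would have let a reader see this. The summaries named in SAP 9.3.2.3 do not give the baseline breakdown.

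**Working it through.** The documents give no figure for this rate, so there is none to reproduce. The check has two parts.

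**1. Does any rule in the plan remove these subjects?**

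- SAP 3.1 sets percentages "with the denominator being the number of subjects in the relevant population with non-missing data", unless otherwise stated. Negative is a recorded grade, not a missing one, and 9.3.2.3 states its own denominator.
- SAP 12 limits reporting to observed data. A Negative grade is observed.
- SAP 3.3.3 takes the highest pre-treatment grade. This lowers the number of Negative baselines but does not exclude them.

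None of them removes a subject whose baseline is Negative.

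**2. What is the effect on the rate?**

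Input from the documents: N = 30 (SAP 2.1). Not in the documents, so assumed: the smear-negative share q, the decrease rate p among smear-positive subjects, and the group sizes. For simplicity, every subject is taken to have a grade at the visit.

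- Reported rate = p × (1 − q)
- Highest reportable rate = 1 − q
- Shortfall = p − p(1 − q) = p × q

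The table uses p of about 60% and N = 30, with exact (Clopper-Pearson) 95% intervals. The last column lets p run from 30% to 80%.

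| Negative at baseline | Among smear-positive | As SAP 9.3.2.3 reports it | Ceiling | Shortfall, points |
|---|---|---|---|---|
| 0 | same as reported | no change | 100% | 0 |
| 2 | 17/28 = 60.7% (40.6–78.5) | 17/30 = 56.7% (37.4–74.5) | 28/30 = 93.3% | 2.0–5.3 |
| 5 | 15/25 = 60.0% (38.7–78.9) | 15/30 = 50.0% (31.3–68.7) | 25/30 = 83.3% | 5.0–13.3 |
| 10 | 12/20 = 60.0% (36.1–80.9) | 12/30 = 40.0% (22.7–59.4) | 20/30 = 66.7% | 10.0–26.7 |

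As an example of the last column, with 5 Negative q = 5/30, so the shortfall runs from 0.30 × 5/30 = 5.0 points to 0.80 × 5/30 = 13.3 points.

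By group, assume 15 subjects each and p = 60% in both. A group with no Negative baselines shows 9/15 = 60% (32.3–83.7). A group with 5 shows 6/15 = 40% (16.3–67.7), although its rate among smear-positive subjects is 6/10 = 60% (26.2–87.8).

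**The case against.** The all-subject proportion is prespecified in both documents and consistent with an analysis of all enrolled subjects. As the share of all subjects whose smear grade fell, it is a legitimate and conservative summary. That stands, and it is why the row should be kept.

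A reader might infer that the rate among smear-positive subjects cannot be recovered from the tables. That goes too far. The decrease count will be printed, and smear conversion is to be presented out of its own smear-positive population, so one count can be divided by the other. The result is approximate, because grades missing at a visit are not accounted for. The replacement tables follow mock shells that are not among the documents, and these may show more than the text of 9.3.2.3 does.

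The size rests wholly on assumption. Under the current schedule a Negative baseline needs up to six negative samples (three at each of two visits), with fewer for early subjects. Nothing in the documents supports 10 in 30 as the likely case.

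The restricted rate has a bias of its own. Baseline is the worst grade over two visits and each follow-up is one visit, so some decreases will appear without real change. In an uncontrolled trial, dropping the subjects who cannot decrease makes this more visible. This stands, and the row needs a footnote.

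A reader might also extend the point to culture grading in SAP 9.3.2.4. The documents do not support that. A positive culture at Screening is required and baseline takes the worst pre-treatment result, so a negative culture baseline should not arise in eligible subjects.

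**Conclusion.** The point holds as a limit on what the planned smear summary can show. Any subject Negative at baseline counts as a non-decrease, no rule in the plan removes that subject, and the rate is capped at the smear-positive share. The loss is p × q. It is zero if no subject is Negative at baseline, and it cannot be sized from the documents. The 60% rate, the counts of 2, 5 and 10 Negative, and the groups of 15 are illustrations only.

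Three stronger readings should be set aside:

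- The prespecified proportion is not an error. It answers a different question from the one a reader may take it to answer.
- No planned group comparison is biased, because none is planned. The rates are descriptive and exploratory.
- The 30% response rate called clinically relevant belongs to the primary endpoint (SAP 9.3.1.1), so no decision turns on this rate.

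The primary and smear-conversion endpoints are unaffected. The change is still worth making, because the rate serves the bacterial-load objective in a pilot meant to inform further phase II planning (Protocol 6.3).

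**What to change.** In SAP 9.3.2.3, at each scheduled visit:

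- Keep the all-subject proportion, labelled as such.
- Add a labelled row giving the decrease rate among subjects with a baseline smear grade above Negative and a grade at that visit, with the exact 95% interval.
- Print by group the number evaluable for that row and the number Negative at baseline.
- Add a footnote that baseline is the worst grade over two visits while each follow-up is one visit, so the restricted rate may be raised.

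The restriction uses a pre-treatment grade, so being smear positive at baseline adds no selection on response. The requirement for a grade at the visit does make the denominator change from visit to visit, which is why the number evaluable must be shown.

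The cost is a sentence or two, one denominator flag and the footnote, with no new data. The interval is usually wider: in the three N = 30 examples the widths are 37.9 against 37.1 points, 40.2 against 37.4, and 44.8 against 36.7.
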